6.9. Treatment Compliance

By-patient listings of randomization schedules and study drug dispensed (include the clinical trial (CT) Lot number), respectively, for the ITT Populations will be provided.

Throughout treatment periods, randomized patients will record information in a Study Drug Administration Log (captured in the Exposure as Collected eCRF page), including the date, time, and anatomical location of administration of investigational product, syringe number, who administered the investigational product, and the reason if the investigational product was not fully administered.

Treatment compliance for each patient per period will be calculated as:

$$\text{Treatment compliance (\%)} = 100 \times \frac{\text{Total number of injections administered}}{\text{Total number of injections prescribed}}$$

Clinical Protocol RHCD:

- For patients who complete Period 2 and receive ixekizumab 20 mg or 40 mg or placebo for ixekizumab 20 mg or 40 mg, the number of injections prescribed (that is, expected) during Period 2 will be equal to 3 (1 injection at Week 0 and 1 injection at Weeks 4 and 8).
For patients who complete Period 2 and receive ixekizumab 80 mg or placebo for ixekizumab 80 mg, the number or injections prescribed during Period 2 will be equal to 4 (2 injections at Week 0 and 1 injection at Weeks 4 and 8).
- For patients who discontinue during Period 2, the number of injections prescribed during Period 2 can be derived from the IWRS study drug dispense dataset.

Protocol Addendum RHCD(2):

- The number of injections for ixekizumab group and placebo group are the same as in the main study ITT Population. For patients who complete Period 2 and receive etanercept, the number of injections prescribed during period 2 will be equal to 12 (1 injection every week from Week 0 to Week 11).
- For patients who discontinue during Period 2, the number of injections prescribed during Period 2 can be derived from the IWRS study drug dispense dataset.

A patient will be considered overall compliant with study treatment within each treatment period if he/she misses no more than 20% of the expected doses, does not miss 2 consecutive doses, and

does not overdose (that is, take more injections at the same time point than specified in the protocol).

Patient treatment compliance, by Period 2, will be summarized. The comparisons between treatment groups during Period 2 will be conducted using Fisher's exact test.

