6.11.3. Additional Analyses of the Co-Primary Outcome

There will be no adjustment for multiple comparisons for additional analyses of the co-primary outcomes.

To support the primary efficacy analysis, the co-primary outcomes, PASI 75 and sPGA (0,1), will be analyzed based on the PPS Population for the Double-Blind Treatment Period (Period 2), comparing ixekizumab versus placebo at Week 12 using Fisher's exact test with NRI.

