6.16. Protocol Deviations

Protocol deviations will be identified throughout the study. Important protocol deviations are defined as those deviations from the protocol likely to have a significant impact on the completeness, accuracy, and/or reliability of the study data, or that may significantly affect subject's rights, safety, or well-being.

The major protocol deviations, which are the subset of the important protocol deviations, are the protocol deviations that might have impact on the efficacy and/or safety results. The impact of major protocol deviations on the efficacy results will be investigated by assessing the robustness of the study results and conclusions to the choice of analysis population, both by including and excluding the data potentially affected by major protocol deviations. As specified in Section 6.1.1, the PPS Population is defined as all randomized patients who do not have major protocol deviations.

Table RHCD.6.12 includes the categories and subcategories of important protocol deviations, whether or not these deviations are major protocol violations, the action to be taken regarding the exclusion of patients from PPS, the source of the deviation identified, and the statistical programming guidance for the clinical study report (CSR).

The number and percentage of patients having important protocol deviation(s) will be summarized within category and subcategory of deviations by treatment group for the ITT Population for the Double-Blind Treatment Period (Period 2).

A by-patient listing of important protocol deviations will be provided.

Table RHCD.6.12. Identification and Action of Important Protocol Deviations

Important Protocol Deviation Category/Subcategory/Study Specific	Action for PPS Analysis	Source to Identify Protocol Deviation ^a	Statistical Programming Guidance for Clinical Study Report
Category: Eligibility			
Subcategory: Inclusion/Exclusion			
[1] No confirmed diagnosis of moderate-to-severe plaque-type Ps for at least 6 months prior to Visit 2	Excluded from PPS	Monitor and Stats	Either from monitor’s list, or, if date of diagnosis of Ps is missing or less than 6 months prior to Visit 2.
[2] PASI score <12 or sPGA <3 or BSA involvement <10% at Visit 1 or Visit 2	Excluded from PPS	Monitor and Stats	Either from monitor’s list, or, If PASI score <12 or sPGA <3 or BSA involvement <10% or any missing at Visit 1 or Visit 2.

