Subcategory: Compliance	Excluded from PPS	Stats	If non-compliant with study medication regimen or over-dose during the treatment period. Note: Non-compliance with therapy is defined to be missing more than 20% of expected doses and missing 2 or more consecutive doses; over-dose is defined as to take more injections at the same time point than specified in the protocol.
Subcategory: Patient took medication not fit for use	Do not excluded from PPS	Monitor	From monitor's list.
Subcategory: Other			
Randomized but did not take any study medication	Excluded from PPS	Stats	If a patient is randomized but does not take any study medication.
Overdose/ Underdose in terms of actual volume of IP	Excluded from PPS	Monitor	From monitor's list.
Category: Safety			
Subcategory: SAEs			
Failure to report within 24 hours of the PI aware	Do not Excluded from PPS	Monitor	From monitor's list.
Category: Informed Consent			
Subcategory: Informed Consent not Obtained/Missing/Late	Excluded from PPS	Monitor and Stats	Either from monitor's list, or, if patient informed consent date is after Visit 1 date or missing informed consent.
Subcategory: Improper Informed Consent	Do not Excluded from PPS	Monitor	From monitor's list.
Category: Administrative/Oversight			
Subcategory: Reg/Ethic Approvals	Excluded from PPS	Monitor	From monitor's list.
Subcategory: Other			
Enrolled in a site with significant GCP noncompliance issue	Excluded from PPS	Monitor	From monitor's list.

Abbreviations: AE = adverse event; BCG = Bacille de Calmette et Guérin; BSA = body surface area; CDRS-R = Children's Depression Rating Scale–Revised; Con-Meds = concomitant medications; C-SSRS = Columbia–Suicide Severity Rating Scale; DV = protocol deviations; eCRF = electronic case report form; GCP = good clinical practice; IgG = immunoglobulin G; IL = interleukin; ITT = intent-to-treat; IV = intravenous; IWRS = interactive web-response system; PASI = Psoriasis Area and Severity Index; PPD = purified protein derivative; PPS = per protocol set; Ps = psoriasis; PsA = psoriatic arthritis; Reg = regulatory; SAE = serious adverse event; sPGA = static Physician Global Assessment; stats = statistics; TB = tuberculosis; TBL = total bilirubin.

^a The term “Monitor” indicates the protocol deviation will be identified by site monitors and entered into monitor’s list using a spreadsheet. The spreadsheet will be exported as Study Data Tabulation Model (SDTM) DV domain.

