The term “Stats” indicates the protocol deviation will be programmed based on data in clinical database by statistical programmers with the statistical programming guidance provided as the last column. The detailed programming specification will be documented in Analysis Data Model (ADaM) specification.

The terms “Monitor and Stats” indicates the protocol deviation will be a combination of monitor’s list (SDTM.DV domain) and statistical programming from clinical database, the deviation will show if either source identifies.

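### SAP Section 6.9 and the Compliance row of Table RHCD.6.12 define non-compliance differently, so a completer who missed one of three doses is non-compliant under the first but not excluded from the per-protocol set by the second

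*SAP*

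**What the plan says.** SAP Section 6.9 gives the rule behind the Period 2 compliance summary. A subject is compliant who "misses no more than 20% of the expected doses, does not miss 2 consecutive doses", and who does not overdose.

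The Compliance row of Table RHCD.6.12 (SAP Section 6.16) removes subjects from the PPS. Its note reads: "Non-compliance with therapy is defined to be missing more than 20% of expected doses and missing 2 or more consecutive doses". Overdose is a separate, alternative trigger in the same row.

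The row's only source is Stats. The table footnote says that a deviation from this source "will be programmed based on data in clinical database by statistical programmers with the statistical programming guidance provided as the last column", and then: "The detailed programming specification will be documented in Analysis Data Model (ADaM) specification". That specification is not among the supplied documents.

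Section 6.16 uses the PPS to judge robustness, "both by including and excluding the data potentially affected by major protocol deviations". Section 6.11.3 gives the analysis: "To support the primary efficacy analysis, the co-primary outcomes, PASI 75 and sPGA (0,1), will be analyzed based on the PPS Population", for ixekizumab against placebo at Week 12.

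**The concern.** Both texts use the same two missed-dose criteria. Section 6.9 lists what a compliant subject must satisfy, joined by *and*. The opposite of that list is failing the first condition *or* the second. The table states the opposite but keeps *and*, so it describes a smaller group. Overdose triggers in both places, so the conflict is confined to missed doses.

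The short schedule makes this more than a matter of wording. With three dosing occasions in Period 2, a single miss is already well above 20%, yet it can never be two consecutive misses. Read literally, the row leaves in the PPS a completer whom the compliance table in the same report counts as non-compliant. The PPS is meant to show the co-primary results without subjects who have major deviations, so this weakens the one analysis built for that purpose.

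**Working it through.** **Inputs.** Section 6.9 prescribes, for Period 2 completers, 3 injections at 20 or 40 mg or matching placebo (one each at Weeks 0, 4 and 8), 4 injections at 80 mg or matching placebo (two at Week 0, one each at Weeks 4 and 8), and 12 weekly injections of etanercept. Section 5.2.1 plans 110 ixekizumab and 55 placebo subjects, with response rates of 80% and 10%.

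**Rules compared**, with overdose set aside because it triggers in both:
- Section 6.9: non-compliant if share missed > 20% *or* at least 2 consecutive misses.
- Table RHCD.6.12: non-compliant if share missed > 20% *and* at least 2 consecutive misses.

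**Ixekizumab and placebo: 2³ − 1 = 7 patterns with at least one miss.**

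| Weeks missed | Share of occasions | Share of injections at 80 mg | Consecutive? | Section 6.9 | Table row |
|---|---|---|---|---|---|
| 0 | 33.3% | 50% | no | non-compliant | not excluded |
| 4 | 33.3% | 25% | no | non-compliant | not excluded |
| 8 | 33.3% | 25% | no | non-compliant | not excluded |
| 0, 8 | 66.7% | 75% | no | non-compliant | not excluded |
| 0, 4 | 66.7% | 75% | yes | non-compliant | excluded |
| 4, 8 | 66.7% | 50% | yes | non-compliant | excluded |
| 0, 4, 8 | 100% | 100% | yes | non-compliant | excluded |

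All 7 are non-compliant under Section 6.9. The row excludes 3, so 4 diverge, whether doses are counted by occasion or by injection.

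**Etanercept: 2¹² − 1 = 4,095 patterns.** Compliant under Section 6.9 are the 12 single misses and the 66 − 11 = 55 non-adjacent pairs, so 4,095 − 67 = 4,028 are non-compliant. The row catches 3,708, leaving 320 that diverge: 11 with exactly two consecutive misses (2/12 = 16.7%) and 120 + 126 + 56 + 7 = 309 with three to six misses, none adjacent. These are counts of patterns, not probabilities.

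**Possible effect on the PPS estimate.** The number of subjects affected is not given, so it is assumed here. Take 165 completers who miss Week 4 and Week 8 independently, each with probability p. The expected number with exactly one of these missed is 2p(1 − p) × 165:
- p = 1%: 0.0198 × 165 = 3.3
- p = 2%: 0.0392 × 165 = 6.5
- p = 5%: 0.095 × 165 = 15.7

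At the planning rates the starting difference is 88/110 − 5.5/55 = 70.0 points. The lowest value after removal takes out ixekizumab responders and placebo nonresponders; the highest takes out the reverse.

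| Removed (ixekizumab + placebo) | Lowest | Highest |
|---|---|---|
| 2 + 1 | 86/108 − 5.5/54 = 69.4 | 88/108 − 4.5/54 = 73.1 |
| 4 + 2 | 84/106 − 5.5/53 = 68.9 | 88/106 − 3.5/53 = 76.4 |
| 11 + 5 | 77/99 − 5.5/50 = 66.8 | 88/99 − 0.5/50 = 87.9 |

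In the least favourable case (77/99 against 6/50, placebo responders rounded up), Fisher's exact p is about 6 × 10⁻¹⁵.

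**The case against.** The strongest reply is that the two rules serve different purposes. Section 6.9 defines compliance for a summary table, while Table RHCD.6.12 carries its own explicit definition for the PPS. Section 6.16 confines PPS exclusion to major deviations, a subset of the important ones, so a narrower rule would fit. The table was also updated from a Trial Issue Management Plan that is not supplied, so the wording may be deliberate. That possibility stands, but the SAP nowhere says that a looser rule was meant. The row would also keep a completer who missed Weeks 0 and 8, two thirds of the doses.

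A second reply is that the stakes are small. This is largely right: the PPS is supportive and superiority is not in doubt. The bounds are extremes; if missing a dose is unrelated to response, the expected shift is about zero. The 7 patterns are not equally likely, and missing Week 0 should be rare in a completer. The all-missed pattern is also excluded by the separate row for subjects who took no study medication. The etanercept counts have little consequence, because the PPS analyses specified are ixekizumab against placebo.

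Third, the row for underdosing by actual volume might catch some of these subjects. It relies on the monitor's list alone, and the SAP does not say that it covers a wholly missed dose.

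**Conclusion.** The two definitions conflict as written, and the concern holds. On the ixekizumab and placebo schedule 4 of 7 missed-dose patterns are classified differently, including every single miss. The consequence is limited to PPS membership, the supportive co-primary analysis on the PPS, and its consistency with the compliance summary. The ITT primary and gated results are untouched.

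This rests on a literal reading of the note and on the footnote that ties programming to it. How the flag was actually coded cannot be confirmed without the ADaM specification. The 3, 6 and 16 subjects used for the bounds are assumptions, and the real number cannot be derived from the documents. The point should be corrected, but it does not threaten the trial's conclusions.

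**What to change.** Use one definition in both places. In the Compliance row of Table RHCD.6.12, make non-compliance more than 20% of expected doses missed *or* two or more consecutive doses missed, with a reference to Section 6.9. If a looser rule for the PPS was intended, say so and justify the difference.

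Then check that the ADaM specification matches the chosen wording. If the flag changes, rerun the ixekizumab-versus-placebo PPS analysis and label it a post-lock correction, since Section 3 records that SAP Version 3 was approved after the primary database lock.

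The cost is one word and a cross-reference, one check of the specification and, only if needed, one supportive rerun. The PPS may become somewhat smaller, by an amount that the documents do not allow us to state.

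A minor tidy-up in the same table: eligibility item [5], marked as not excluding, carries the same late-consent-date trigger on which the Informed Consent row already excludes. Remove the trigger from item [5]; this may change the count of deviations reported under that item, but the Informed Consent row still excludes those subjects.

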6.17. Interim Analyses and Data Monitoring

Two planned interim analyses will be conducted with an conditional third dependent upon enrollment.

A staggered approach to enrollment by weight group will be used so that a minimum of 15 subjects >12 years and >50 kg will be enrolled and safety evaluated for the initial 12 weeks of dosing before opening enrollment in the middle weight group (25 to 50 kg).

When approximately 15 subjects have enrolled in the middle weight group and completed up to Week 12, an analysis of all available PK data will be conducted to confirm that exposures are within the range expected. All safety data from these subjects will also be analyzed at this time in addition to select efficacy data. Doses for the remaining subjects in the study will be confirmed, based on these analyses. Once confirmed, all weight groups will be open for enrollment of the remaining subjects needed to complete the study.

The first interim analysis will be conducted after approximately 15 subjects in the 25- to 50-kg weight group have completed to Week 12. Pharmacokinetic, safety, and efficacy data on all subjects will be evaluated during this interim. The analysis will include all data available at this time – that is, it will include data from subjects in both weight groups who have enrolled at the time of the interim. The analysis of the data will be conducted by statisticians and PK/PD scientists external to the study team (statistical assessment center). The statistical assessment center will provide the analyses to a data monitoring committee (DMC) consisting of members external to Lilly. The DMC will recommend whether changes to weight-based dosing are necessary, based on the analysis. This committee will consist of 2 physicians external to Lilly, a pediatrician and a dermatologist, a statistician external to Lilly, and an nonvoting PK/PD member internal to Lilly, but external to the study team. No member of the DMC may have contact with study sites. Only the DMC is authorized to evaluate unblinded interim efficacy and safety analyses. Study sites will receive information about interim results ONLY if they need to know for the safety of their subjects.

Study sites will receive information about interim results ONLY if they need to know for the safety of their subjects.

The second interim database lock and unblinding will occur and the analysis will be performed at the time (that is, a cutoff date) the last subject completes Study Period 2 (Week 12) or ETV. This interim database lock will include all data collected by the cutoff date including follow-up data from subjects that have begun Periods 3, 4, or 5. Because the study will still be ongoing at the time of this database lock, the analysis will be referred to as an interim analysis. This interim analysis includes the final analysis for the Double-Blind Treatment Period (Period 2) of the study; therefore, there is no alpha adjustment due to this interim analysis. The DMC is not needed for this interim analysis.

Additional analyses and snapshots of study data may be performed during and/or after completion of Period 3 and/or Period 4 to fulfill the need for regulatory interactions or publication purposes.

Enrollment of each geographic region will be closely monitored. If 120 subjects from the United States and Canada complete the 12-week Double-Blind Randomized Period, and if other regions are behind in reaching their enrollment goal, an additional interim analysis may be conducted to include only the subjects from the United States and Canada to meet the US submission timeline. The DMC is not needed for this interim analysis. The analysis specified in this SAP for Period 2 will be conducted using the ITT Population and Safety Population subsetting on subjects from the United States and Canada and removing the term “region” from the analysis models. There will be no alpha adjustment applied as this will be considered the primary analysis for some regulatory agencies. The details will be documented in the unblinding plan.

A final database lock will occur after the Post-Treatment Follow-Up Period is completed.

6.18. Planned Exploratory Analyses

The following analyses will be conducted for exploratory purposes and are not intended to be included in the CSR.

6.18.1. Psychometric Analyses of the Itch NRS

Following the examination of the distributional characteristics of measures, the following psychometric properties of the instruments will be evaluated: test-retest reliability; convergent validity; known-groups validity; and sensitivity to change (responsiveness) using anchor- and distribution-based methods.

6.18.1.1. Descriptive Statistics

Descriptive statistics (sample size, mean, standard deviation [SD], minimum, median, maximum, and % missing) will be calculated for the Itch NRS, including scores from Baseline to Week 12. The frequency distributions for Itch NRS responses will be calculated at Baseline and Week 12. Floor and ceiling effects will be evaluated at Baseline. A cut-off of >25% will be used to indicate floor/ceiling effects (McHorney et al. 1994).

6.18.1.2. Test-Retest Reliability

Test-retest reliability has been emphasized by the Food and Drug Administration (FDA) as an important aspect of reliability in the FDA Patient-Reported outcome (PRO) Guidance (FDA 2009). Test-retest reliability reflects the ability of the instrument to give reproducible results when the clinical state is stable and indicates the degree to which a measure produces consistent results over several administrations. Test-retest reliability will be assessed using intra-class correlations coefficients (ICCs) and paired sample t-tests among stable patients only. The ICC will be used to assess the association between Itch NRS at Week 0 and Week 1 in the subsample of placebo arm patients with the same rating on the sPGA at Week 0 and Week 1.

Intra-class correlations coefficients range from 0 to 1.0, with higher scores indicating a more stable instrument. The hypothesis is that there will be no significant differences in scale scores when there is no change in disease status. An ICC of ≥ 0.70 will be considered substantial agreement (Nunnally and Bernstein 1994).

6.18.1.3. Construct Validity

6.18.1.3.1. Convergent and Discriminant Validity

Construct validity is the degree to which a measure is related to other measures or constructed in a manner that is consistent with theory. *Convergent validity* involves demonstrating that different measures of the same concept substantially correlate, while *discriminant validity* demonstrates that concepts that are supposed to be unrelated are, in fact, unrelated.

Convergent validity will be assessed by Pearson correlations and Spearman rank-based correlation coefficient at baseline and at Week 12 between scores of the Itch NRS and other assessments, including PASI, sPGA, PatGA, DLQI (assessed in patients aged >16 years), and CDLQI (assessed in patients aged 6-16 years).

Cohen's conventions will be used to interpret the absolute value of the correlation results, where a correlation >0.5 is large, 0.3 to ≤0.5 is moderate, 0.1 to <0.3 is small, and <0.1 is insubstantial (Cohen 1988). It is hypothesized that small-to-moderate correlations at baseline and moderate-to-large (≥0.30) correlations at Week 12 are expected between the Itch NRS and PASI, sPGA, PatGA, and DLQI / CDLQI total scores.

Additionally, convergent and discriminant validity will be assessed by Pearson correlation and Spearman rank-based correlation at baseline and at Week 12 between scores of the Itch NRS and the DLQI / CDLQI 6 domains: Symptoms and Feelings, Daily Activities, Leisure, Work and School, Personal Relationships, and Treatment (note the CDLQI domains are Symptoms and Feelings, Sleep, Leisure, School or Holidays, Personal Relationships, and Treatment). It is hypothesized that the Itch NRS will correlate higher with the DLQI / CDLQI Symptoms and Feelings domain than with the other 5 DLQI domains.

